MOVE! is the largest weight management program in the U.S., designed to encourage healthy eating behavior and increase physical activity in Veterans who are more likely to be overweight or obese with poor diet,^{5,6} and self-report disability and high numbers of comorbid conditions.^{6,18} Participation in MOVE! is associated with successful short-term health improvements including weight loss and, as participation increases, greater improvements in weight and diet occur.¹⁹ However, only 25% of MOVE! participants engage in sustained participation.¹⁹ Gerofit is another popular national VA program that targets meeting American College of Sports Medicine (ACSM) physical activity guidelines in older adults with dysmobility. We previously published that in Gerofit, despite clinically significant improvements in mobility and high satisfaction with the program, only 53% of older adults remain active in participation at 3-months.²⁰ We find that 71% of all dropouts occur within the first 3 months of Gerofit. These data demonstrate that even expert-led, well-established lifestyle interventions, targeted to older Veterans with dysmobility have a low adherence/retention rates over several months. Peer leaders may be one way to improve adherence to a lifestyle program.

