3.3. Study Endpoints

Primary outcome: To determine the feasibility and acceptability of a 12-week peer-led intervention in older Veterans with dysmobility (N=10/site).

Secondary outcomes:

- a) To assess mobility and function, we will assess a standard battery of functional assessments, including strength, balance, and endurance before and after the 12-week intervention.
- b) To examine cardiometabolic risk factors. We will assess BMI, body composition, and resting blood pressure before and after the 12-week intervention.
- c) To examine psychological health. We will assess quality of life, fatigue, sleep quality, dietary intake and physical activity, and depression before and after the 12-week intervention.

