4.3.2 Data Collection and Follow-up for Withdrawn Subjects

If subjects are withdrawn prematurely from the study, appropriately designated research staff will make efforts to collect data throughout the protocol defined follow-up period for that subject. If participants decided to withdraw from the study, study staff will attempt to conduct an exit interview to request reasons for withdrawal and ways to improve the program.

If a subject withdraws consent to participate in the study, attempts will be made to obtain permission to

record data up to the protocol-described end of subject follow-up period.

Investigator and designated research staff make it a high priority to obtain data on all subjects lost to follow up. Lost to follow up will be defined as a subject missing 3 or more consecutive visits without reasonable explanation, not answering or responding to 3 follow up phone calls to subject or emergency contacts, or returned receipt of 1 certified letter.

5. Study Protocol

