5.2.4 12-Week (Post) Assessments: All tests as described below in the baseline assessment will be repeated after the 12-week intervention. Additionally, a post intervention exit interview (both quantitative and qualitative questions) will be conducted by a research team member to obtain direct feedback on participant experience (i.e., program enjoyment, lesson applicability, confidence and willingness long-term to implement the behavior changes, and identification of additional barriers not addressed). This interview is anticipated to take 20-25 minutes and will be done/recorded with the participants permission on VA Microsoft teams by study staff.

6. Study Procedures

All subjects will undergo baseline testing and test after 12 weeks of the intervention as described below. All study procedures will be performed at the Baltimore VA.

6.1. Feasibility and Acceptability. A flow chart (i.e., consort chart) will be prepared to identify and summarize issues in recruitment and retention (i.e. record total numbers screened, numbers excluded with reasons for non-participation, timing and frequency of dropout, etc.). Acceptable recruitment is defined as 100% of total targeted enrollment within two months of initiating recruitment efforts. Retention will be assessed by frequency count of drop-outs; 80% retention will be considered acceptable. We will examine attrition, and perform qualitative exit interviews whenever feasible. The Usage Rating Profile- Intervention (URPI) feasibility and feasibility subscales will be utilized to assess both peer leaders and participants response to the intervention. We will define successful adherence as participants completing at least 75% of all sessions. We also will evaluate a random sampling of 30% of peer leader sessions to evaluate whether peer leaders accurately covered all prescribed material for each topic.

6.2. Body Composition: Standing height and weight (light clothing, without shoes) will be measure using a calibrated digital scale and body mass index calculated as weight [kg] /height squared [m²]. Total and regional fat mass, lean tissue mass, % body fat, bone mineral content, and bone density will be determined by dual-energy x-ray absorptiometry (DXA).

6.3. Dietary Intake: Instruction on completing a self-administered 24-hour recall will be provided to participants by a Registered Dietitian. Food recall will be entered and analyzed for macronutrient and

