6.6. Statistical Plan

A flow chart (i.e., consort chart) will be prepared to identify and summarize issues in recruitment and retention (i.e. record total numbers screened, numbers excluded with reasons for non-participation, timing and frequency of dropout, etc.). Acceptable recruitment is defined as 100% of total targeted enrollment within two months of initiating recruitment efforts. Retention will be assessed by frequency count of drop-outs; 80% retention will be considered acceptable. Examination of attrition, along with qualitative interviews (whenever feasible). The Usage Rating Profile- Intervention (URPI) acceptability and feasibility subscales will be utilized to assess both peer leaders and participants response to the intervention. We will define successful adherence as participants completing at least 75% of all sessions. We also will evaluate a random sampling of 30% of peer leader sessions to evaluate whether peer leaders accurately covered all prescribed material for each topic. The focus in a feasibility pilot study like this is to estimate the magnitude of potential impact. Data will be inspected for out-of-range values, missing data, and internal consistency (when relevant). Clinical outcomes of interest are changes in diet quality and mobility after the 12-week intervention. Data from this pilot will be compared to changes in Gerofit. Similar changes in mobility with higher adherence and retention will indicate that long term success is feasible for the program and warrant a longer duration trial. Summary statistics with confidence intervals will be calculated to describe average levels and trajectories of clinical outcomes over time. Baseline variables will be summarized, and frequency distributions will be examined for unusual data distributions or data points.

7. Safety and Adverse Events

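### The plan does not say when the URPI is given or whether leavers complete it, so the acceptability score will probably come mainly from completers and could be too favourable

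*Combined protocol and SAP*

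**What the plan says.** Section 3.3 gives the primary outcome as "To determine the feasibility and acceptability of a 12-week peer-led intervention in older Veterans with dysmobility (N=10/site"). The two components are named together, without weights.

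The URPI is the only named scale for rating the intervention, and it is described twice. Section 6.1: "The Usage Rating Profile- Intervention (URPI) feasibility and feasibility subscales will be utilized to assess both peer leaders and participants response to the intervention". Section 6.6: "The Usage Rating Profile- Intervention (URPI) acceptability and feasibility subscales will be utilized to assess both peer leaders and participants response to the intervention". Neither gives a time point, a cut-off or a rule for missing ratings.

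On timing in general, section 6 says "All subjects will undergo baseline testing and test after 12 weeks of the intervention as described below". Section 5.2.4 adds, at week 12, "a post intervention exit interview (both quantitative and qualitative questions) will be conducted by a research team member to obtain direct feedback on participant experience".

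For those who withdraw, section 4.3.2 says "study staff will attempt to conduct an exit interview to request reasons for withdrawal and ways to improve the program". The same section promises efforts to go on collecting data through the follow-up period. Section 6.1 adds qualitative exit interviews when these are feasible. The URPI is not mentioned in either place.

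**The concern.** A person can rate a response to the intervention only after being exposed to it. Of the two scheduled testing times, that leaves week 12. Someone who has left by then has no scheduled occasion to complete the URPI. The contact specified for leavers asks for reasons and suggestions and does not ask for a score.

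If people who dislike the programme are more likely to leave, an average over those still present at week 12 overstates how acceptable the programme was to the Veterans who enrolled. The background section leads one to expect substantial loss. In Gerofit, 53% were still active at 3 months, and "We find that 71% of all dropouts occur within the first 3 months of Gerofit".

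The wording of section 6.1 adds a practical risk. Staff who follow it literally would collect the feasibility subscale and miss the acceptability subscale that section 6.6 intends to use.

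**Working it through.** **Timing and population, from the text**

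- Section 6 schedules testing at baseline and after 12 weeks. Only the second follows exposure. No section gives another URPI time.
- The week-12 interview (5.2.4) has quantitative and qualitative questions. The attrition interview (6.1) is qualitative only, and the withdrawal interview (4.3.2) is only attempted.
- Section 3.3 attaches 10 per site to the primary outcome. Section 3.1 enrols 15 Veterans per site and gives 10 as the number expected to complete. The denominator suggested is therefore the completers, although no section states it as an analysis rule.

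**Size**

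The documents give no expected URPI result, so there is no figure to reproduce. Inputs for *d*, the share unrated if no leaver is rated:

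- 80% retention called acceptable (6.1, 6.6): *d* = 0.20
- goal of 10 of 15 per site, 20 of 30 overall (3.1): *d* = 1/3
- 53% active at 3 months in Gerofit (1.1): *d* = 0.47

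Assumptions, not from the documents: the share finding the programme acceptable is 80–90% among completers (*Pc*) and 0–50% among leavers (*Pd*).

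All-enrolled value = (1 − *d*)·*Pc* + *d*·*Pd*. The completers-only value is *Pc*. The bias is the difference, *d*·(*Pc* − *Pd*). The smallest gap is 80 − 50 = 30 points and the largest is 90 − 0 = 90 points.

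| Scenario | *d* | Unrated of 30 | Bias, smallest gap | Bias, largest gap |
|---|---|---|---|---|
| 80% retention | 0.20 | 6 | 0.20 × 30 = 6 | 0.20 × 90 = 18 |
| 10 of 15 per site | 1/3 | 10 | 30/3 = 10 | 90/3 = 30 |
| Gerofit 53% | 0.47 | about 14 | 0.47 × 30 = 14.1 | 0.47 × 90 = 42.3 |

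If *Pd* = *Pc*, the bias is 0 in every row.

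For a mean score the same formula applies in SD units. With an assumed completer–leaver gap of 0 to 1.5 SD, the bias is 0 to 0.30 SD, 0 to 0.50 SD and about 0 to 0.71 SD.

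**If some leavers are rated**

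With a share *r* of leavers rated, observed = [(1 − *d*)·*Pc* + *d*·*r*·*Pd*] / [(1 − *d*) + *d*·*r*]. Take *Pc* = 90% and *Pd* = 30% as an illustration.

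- *r* = 0: the observed value is 90%, against 78%, 70% and 61.8% for all enrolled. The bias is 12, 20 and 28 points.
- *r* = 0.5: the observed values are 83.3%, 78.0% and 71.6%. The bias is about 5, 8 and 10 points.
- *r* = 1: the bias is 0.

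**Lower bound**

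Counting every unrated leaver as unfavourable gives (1 − *d*)·*Pc*. With *Pc* = 90% this is 72%, 60% and 47.7%.

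**The case against.** Several stronger readings are tempting, and the documents do not support them.

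- *The URPI can only be scored at week 12.* This is an inference. Section 6.1 contains items collected outside the two testing visits, such as attendance, dropout timing and session fidelity. The separate questionnaires document is not available here. Nothing bars giving the URPI at withdrawal.
- *Leavers never rate the programme.* Section 4.3.2 promises efforts to collect data through follow-up and makes subjects lost to follow-up a priority. Section 11.3 pays separately for the 12-week assessments. Leaving the sessions need not mean missing the rating. Still, these are efforts only, and none names the URPI.
- *The score is biased upward.* The bias depends on an unknown gap. Section 1.1 lists access and disabling health conditions among the barriers to diet and activity, so leaving need not mean dislike.
- *The Gerofit figures show that dissatisfied people leave early.* The 3-month window spans this whole 12-week intervention. The passage gives no reasons for leaving.
- *Acceptability is half of the primary outcome.* No weights are given, and section 3.2 also lists satisfaction, attendance and engagement.
- *A programme that many people left would still look successful.* Retention is judged against 80% and adherence against 75% of sessions, and both are reported. The rule in section 6.6 for a longer trial uses mobility, adherence and retention, and does not use the URPI.

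These replies limit the point. They do not supply a URPI score for leavers, a denominator or a missing-data rule.

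**Conclusion.** The point holds as a gap in the plan with a likely direction of error. Bias is not demonstrated. Followed as written, the plan will most likely yield an acceptability score drawn mainly from completers, and that score will be too favourable if leavers rate the programme lower. The ranges calculated above rest on the assumed shares for completers and leavers and on no leaver being rated, so they show what is possible and do not forecast the result.

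The consequence is confined to how the acceptability component is reported, because separate retention and adherence figures would partly reveal dissatisfaction. The change is still worth making before enrolment, since early ratings from people who leave cannot be recovered later. The mismatch between sections 6.1 and 6.6 is a plain slip. The section 6.1 heading and section 6.6 show what was meant.

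**What to change.** In sections 6.1 and 6.6:

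1. State that the URPI acceptability and feasibility subscales are given at one early session, at week 12, and at the withdrawal exit interview or lost-to-follow-up contact.
2. Report the number rated out of all enrolled, and say how many left before attending any session.
3. Show the week-12 completers' score next to a summary that includes leavers' ratings, stating when each rating was taken, because early, exit and week-12 ratings are not interchangeable.
4. Add a sensitivity analysis that counts unrated leavers as unfavourable. The plan has no URPI cut-off, so define in advance what counts as favourable.
5. Correct section 6.1 to name the same subscales as section 6.6.

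The cost is protocol wording, a few minutes of burden at a session or contact already planned, and an acceptability figure that may be less favourable.

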6.6. Statistical Plan

A flow chart (i.e., consort chart) will be prepared to identify and summarize issues in recruitment and retention (i.e. record total numbers screened, numbers excluded with reasons for non-participation, timing and frequency of dropout, etc.). Acceptable recruitment is defined as 100% of total targeted enrollment within two months of initiating recruitment efforts. Retention will be assessed by frequency count of drop-outs; 80% retention will be considered acceptable. Examination of attrition, along with qualitative interviews (whenever feasible). The Usage Rating Profile- Intervention (URPI) acceptability and feasibility subscales will be utilized to assess both peer leaders and participants response to the intervention. We will define successful adherence as participants completing at least 75% of all sessions. We also will evaluate a random sampling of 30% of peer leader sessions to evaluate whether peer leaders accurately covered all prescribed material for each topic. The focus in a feasibility pilot study like this is to estimate the magnitude of potential impact. Data will be inspected for out-of-range values, missing data, and internal consistency (when relevant). Clinical outcomes of interest are changes in diet quality and mobility after the 12-week intervention. Data from this pilot will be compared to changes in Gerofit. Similar changes in mobility with higher adherence and retention will indicate that long term success is feasible for the program and warrant a longer duration trial. Summary statistics with confidence intervals will be calculated to describe average levels and trajectories of clinical outcomes over time. Baseline variables will be summarized, and frequency distributions will be examined for unusual data distributions or data points.

7. Safety and Adverse Events

7.1. Recording of Adverse Events

Throughout the study, the investigator or study staff will seek information about adverse events by specific questioning and, if appropriate, by examination. Information on all AEs will be recorded immediately in the source document, and also in the appropriate case report form (CRF). AEs will be reviewed by Site Investigator on a monthly and ad hoc basis, depending on severity and expected/unexpected nature of the event. All AEs occurring during the study period will be recorded. The clinical course of each event will be followed until resolution, stabilization, or until it has been determined that the study treatment or participation is not the cause.

7.2 Reporting of Serious Adverse Events and Unanticipated Problems

Each participant will be evaluated for any adverse events (AE). Any incidents, experiences, and outcomes either reported by the subject to the PI or designated research staff or medical staff caring for the subject, and which meet AE criteria will be documented. Any AE reported as serious (SAE) will be reported to the IRB and, if deemed appropriate by PI, SAE and or unanticipated risks to subjects or others (UPIRSO) may be reportable to the Baltimore Pepper Center Data Monitoring Committee. All AE that are not serious will be summarized annually and submitted to the IRB and R&D Committees.

SAE will be reported per IRB policy and procedure. Events that do not involve AE or SAE, and which are a result of study participation are also promptly reported to the IRB per local policy. The report will include a description of the event, when and how it was reported, as well as any official chart records or documentation to corroborate the event or the reporting of the event. All AE will be graded as mild, moderate, or severe. Any action resulting in a temporary or permanent suspension of this study (e.g. local site IRB actions) will be reported to the IRB and study sponsor.

7.3 Medical Monitoring

The Sponsor (or investigator initiating the study) will review the safety and progress of this study on a monthly basis or when needed if protocol deviations/violations or AEs occurs.

The PI and or Co-PI will review source documentation in the research record and or medical record when study coordinator provides an electronic alert or secure email to review.

8. Data Handling and Record Keeping

8.1. Confidentiality

Information learned about all subjects will be kept confidential. All data and protected health information in paper form will be kept confidential by assigned uniquely coded identifier and kept secured (password protected and/or double locked). Subjects will not be identified in any way in any publication.

8.2. Source Documents

Source data will be originated both electronically and on paper. No VA sensitive information will leave the VA protected environment. Sensitive VAMHCS electronic data for this study will remain securely behind the VA firewall and will only be accessible through secure VA computer accounts. The network and computer files are only accessible by authorized study team members. Electronic research files are backed up regularly. All sensitive VA paper records will be securely stored in locked file cabinets behind locked doors in the GRECC. All research related electronic data is stored coded and subject identifiers, such as names, are not stored in the same files that contain the research data.

Only de-identified electronic data are sent to and received from the San Antonio VA for further analysis. The electronic data is stored in either VA Qualtrics or VA RedCap, which is hosted by VINCI. VA Qualtrics, or paper surveys maybe used to collect questionnaires and then transferred to VA RedCAP. This will be decided by participant preference.

All entries will be printed legibly in black ink. Erasures and white-out material are prohibited. If any entry error has been made on paper, to correct such an error, draw a single straight line through the incorrect entry and enter the correct data above it. All such changes must be initialed and dated. For clarification of illegible or uncertain entries, print the clarification above the item, then initial and date it.

8.2.1 Research Electronic Data Capture (REDCap) and origination of electronic source data

De-identified medical histories, physical exams, concomitant medications, checklists of consent processing, and documentation of eligibility criteria may be originated electronically in REDCap. Then REDCap forms will be downloaded in PDF format and printed to file in the paper participant record at the research site. Other electronically originated data in REDCap include: adverse event (AE) assessments and AE logs, enrollment logs, protocol deviation logs, and other study management checklists. Other electronic medical record data (VA CPRS) including pre-existing history, exams, medication lists, and such may be accepted as source data.

All missing data will be routinely queried, corrected, and or explained. If a space on the CRF is left blank because the procedure was not done or the question was not asked, write “N/D”. If the item is not applicable to the individual case, write “N/A”.

8.2.2 Paper source data

Paper source data will be entered into the REDCap database. All missing data will be routinely queried, corrected, and or explained. If a space is left blank on paper because the procedure was not done or the question was not asked, write “N/D”, initialed and dated by the staff member. If the item is not applicable to the individual case, write “N/A”.

- Questionnaires and assessments may be originated electronically in either VA Qualtrics or VA REDCap. This will be done only after written informed consent on paper copies is completed. If surveys are done in VA Qualtrics or if it is otherwise necessary to originate survey data on a paper source that data will be transferred to REDCap for calculation, data management and analysis. Paper sources will be filed in paper subject records.

8.2.3 Handwritten entries

All handwritten entries will be created contemporaneously to the visit or phone call, and legibly in blue or black ink. Erasures and white-out material are prohibited. If any entry error has been made on paper, to correct such an error, draw a single straight line through the incorrect entry and enter the correct data above it. All such changes must be initialed and dated. For clarification of illegible or uncertain entries, print the clarification above the item, then initial and date it.

